4.5 Unscheduled Visits

Due to the complexity of the study, no unscheduled visits will be permitted.

4.6 Subject Completion/Withdrawal

For subjects who were naïve to pancreatic enzyme medication at the start of the study, at the end of participation in the study (all collections are complete for Study Visit #2) Creon™ will be discontinued and they will resume their usual care without pancreatic enzyme medication. For subjects who were receiving pancreatic enzyme medication prior to the start of the study, at the end of participation in the study (all collections are complete for Study Visit #2), Creon™ will be discontinued and they will resume their usual care and will resume the pancreatic enzyme product and dose they were receiving before the study began.

Subjects may withdraw from the study at any time without prejudice to their care. They may also be discontinued from the study at the discretion of the Investigators for lack of adherence to study treatment or visit schedules, or adverse events. The Investigators or the Sponsor may also withdraw subjects who violate the study plan, or to protect the subject for reasons of safety or for administrative reasons. It will be documented whether or not each subject completes the clinical study. If the Investigator becomes aware of any serious, related adverse events after the subject completes or withdraws from the study, they will be recorded in the source documents and on the CRF. All subjects withdrawn from the study will receive a follow up phone call weekly for one month.

We expect investigator-based subject withdrawal to be rare. Subjects who experience an unexpected increase in ostomy or stool output during or following a baseline study will require additional monitoring of serum electrolytes and stools or ostomy output as needed. Those subjects who require changes to their parenteral nutrition for greater than three days or initiation of intravenous hydration and electrolyte repletion for greater than three days will not have a repeat MBT. These subjects will not require withdrawal from the study if both they and their primary care team for SBS agree to continued participation. Once electrolytes are stable, they will continue the study.

If a subject withdraws from the study for any cause, baseline data will be used for analysis.

5 STUDY EVALUATIONS AND MEASUREMENTS

5.1 Screening and Monitoring Evaluations and Measurements

5.1.1 Medical Record Review

Variables that will be abstracted from the medical chart (paper or electronic):

- History of a prior small bowel resection
 - If small bowel resection occurred under 18 years of age, subjects must have dependence on parenteral nutrition for at least three months following small bowel resection
 - If small bowel resection occurred at 18 years of age or older, subjects must have 200 centimeters or less of residual bowel length and must have more than 3 bowel movements per day following small bowel resection
- Date of birth - Age 4 years to 75 years
- Sex
- SBS diagnosis: estimated length of residual bowel, number and purpose of operations, presence or absence of ileocecal valve
- Most recent enteral nutrition and parenteral nutrition regimen
- Medical comorbidities that affect the gastrointestinal tract and impact absorption or digestion
- Current diagnosis of a motility disorder (i.e. chronic pseudo-obstruction, severe gastroparesis)
- Current diagnosis of cholestatic liver disease defined as a serum conjugated bilirubin greater than 1.0 mg/dL
- Current listing status for intestinal transplant
- History of pancreatic enzyme use
- History of a pork, soy, or safflower oil allergy
- History of gout, chronic renal failure requiring dialysis or listed for kidney transplant, or fibrosing colonopathy
- All medications, particularly medications that alter fat absorption (weight loss medications, bile acid sequestering agents, or ursodeoxycholic acid)
- All allergies
- History of use of pancreatic enzymes
- Hospitalizations in the past 2 weeks
- Emergency room visits or unscheduled sick visits in the last month

5.1.2 Laboratory Evaluations

Serum 25-dihydroxyvitamin D and pre-albumin will be assessed at CHOP laboratories. PIVKA II ([name], Tuft's University, Medford, MA) and/or undercarboxylated osteocalcin % (UCOC %) will be assessed for vitamin K status ([name], Yale University, New Haven, CT). Prealbumin, zinc, serum retinol (vitamin A), α tocopherol (vitamin E), and selenium will be assessed at CHOP Laboratories using standard techniques. A fatty acid profile will be assessed by Mayo Medical Laboratories (Rochester, MN). This will provide data on baseline malabsorption and nutritional

status resulting from short bowel syndrome that may be improved with pancreatic enzyme medication in subjects. Safety measures include results from serum basic metabolic panel (BMP), hepatic function panel, and complete blood count with differential (CBC) performed at CHOP Laboratories using standard techniques. The hepatic function panel will provide serum albumin, total protein, bilirubin, and liver enzymes to provide additional liver and nutritional status information. Serum citrulline, IGF-1, IGF BP3, GLP-2, GH, and CCK levels (MBT/CCK subset only) will be assessed by the CTRC Core Laboratory at CHOP. All individuals from institutions outside of CHOP will receive only coded, not readily identifiable, samples for analyses and are not otherwise engaged in human subjects' research.

5.1.2.1 Pregnancy Testing

A urine pregnancy test will be performed for pre-menopausal female subjects who are 9 years of age or older.

5.1.3 Other Evaluations and Measures

Dietary intake: A twenty-four hour dietary recall will be obtained after written, informed consent is obtained. This may be completed at study visit 0 or study visit 1. Information on parenteral nutrition and enteral nutrition will be obtained.

Three day weighed food records will be obtained at baseline and while on PERT. Calories, macronutrient content, and micronutrient content will be calculated based on dietary records. All subjects will be provided with scales, spoons, and other supplies needed for accurate collection of dietary data. Analysis of the dietary records will be conducted with the assistance of the CTRC staff and Bionutrition Unit. In particular, dietary intake will be analyzed using Nutrition Data System (NDS) for Research software version 2012 developed by the National Coordinating Center (NCC, University of Minnesota, Minneapolis, MN)

Anthropometric Assessment: Height and weight will be measured for each subject and BMI will be calculated. For subjects under 20 years of age, height, weight, and BMI Z scores will be calculated using growth charts from the Centers for Disease Control and Prevention (CDC)²². Anthropometric techniques will be measured using the methodologies described by Lohman et al²³. Weight (0.1 kg) will be measured on a digital electronic scale (Seca, Munich, Germany) and height (0.1 cm) will be measured using a stadiometer (Holtain, Crymych, UK). In order to assess subcutaneous fat stores, skinfold thickness of the triceps, biceps, subscapular, and suprailiac areas will be measured (0.1 mm) with a skinfold caliper. Total body composition, total free fat mass (FFM) and fat mass (FM) and percent body fat (%FAT), will be assessed by the skinfolds using prediction equations adapted for children, adolescents, and adults^{50, 51}. Mid upper arm circumference will be measured with a fiberglass tape (0.1 cm). Upper arm muscle Z scores and fat area Z scores will be determined for each subject. All anthropometric assessments will be performed once at the study visit #1.

Body Composition: Body composition will be assessed with dual-energy x-ray absorptiometry (DXA) (Delphi A, Hologic, Inc., Bedford, MA) for subjects only at study visit #1. DXA uses very low-dose x-ray exposures (3 mrem) and measurements are rapid, making this a suitable technique for use in children. We will attempt to obtain a DXA scan in subjects of all ages. Standard positioning and clothing techniques are used. Quality control scans are performed daily using a simulated L1-L4 lumbar spine made of hydroxyapatite encased in epoxy resin, and a whole body composition phantom. A difference of >1.5% from the standard will be deemed out-of-range requiring servicing by the manufacturer. The scans will be analyzed to generate traditional DXA measures: whole body

Area, BMC and areal-BMD (gm/cm²). In our institution, the in vitro CV is less than 0.6% and the in vivo coefficient of variation in adults is less than 1%. A urine pregnancy test will be performed on female subjects who are pre-menopausal prior to the scan. Pregnant subjects will not be scanned and will leave the study.

Gastric and Stool pH: Stool pH will be measured at study visit #1 and #2 as a screen for gastric acid hypersecretion. Gastric pH will be measured study visit #1 and #2 if subjects have a gastrostomy tube or a nasogastric tube. This will be performed by the CTRC Core Laboratory at CHOP.

Fecal elastase: Pancreatic function will be assessed by fecal elastase-1 at study visit #1 only to determine the level of pancreatic enzyme activity in the stool²⁴ (Joli Diagnostics, Williamsville, NY). Subjects will be provided with the stool collection kit and proper instructions and supplies, and samples will be collected during the day of the visit if possible. If subjects are unable to produce a stool sample at study visit #1, they will be given supplies to collect a stool sample at home within two days following the visit. This stool sample will be frozen and returned on the day of study visit #2. The stool sample will be stored at -20°C, and analyzed with a monoclonal enzyme-linked immunosorbent assay (ARUP Laboratory, Salt Lake City, UT).

Home Environment and Health Questionnaire: The questionnaire will be administered via interview by the research staff at Study Visit #1, and will consist of two sections. The Health History section has general questions about the subject's health history including documentation of medical history, recent hospital admissions and illnesses, medication, history of pancreatic enzyme supplementation, parenteral nutrition, and nutrient supplement use. A Home Environment section describes aspects of environment, such as education and income level, whether on Medicaid/Medicare and household size to describe the demographic characteristics. In addition to subjects' contact information (name, address, phone numbers); contact information from two additional contacts will be collected to maintain contact with the subject in the event that the subject cannot be contacted at their primary residence.

Quality of Life Questionnaires: In order to assess the health-related quality of life (QOL), validated questionnaires will be administered to all subjects at Study Visit #1. For all subjects 18 years of age and older, the Medical Outcomes Study 36-Item Short-Form Health Survey (MOS SF-36), a standardized, validated health survey will be administered. The MOS SF-36 covers physical functioning, bodily pain, general health perception, vitality, social functioning, emotional and mental health domain²⁵. For subjects between 4 and 17.9 years of age, the Pediatric Quality of Life Inventory (PedsQLTM) is a validated health survey that will be administered. For subjects who are 4 years old, a parent or legal guardian only will complete a proxy-report. For subjects between the ages of 5 and 17.9, both the subject and the parent or legal guardian will complete a survey. The PedsQLTM addresses physical, emotional, social, and school functioning²⁶.

Adherence: Adherence to pancreatic enzyme medication for subjects will be assessed at Study Visit #2 and #3 and by phone calls. This time will also be used to trouble-shoot any barriers to adherence, and also to collect information on adverse events experienced during the course of the study.

Adverse Events Diary: Subjects will be asked about all adverse events at Study Visit #1, Study Visit #2, and Study Visit #3 and asked to rate by intensity (mild, moderate, severe). Serious adverse events will be reported as per various policies in a timely manner to CHOP IRB, and CTRC.

5.2 Efficacy

5.2.2. Diagnostic tests, Scales, Measures

Coefficient of fat absorption (CFA): The coefficient of fat absorption (CFA %) will be calculated based on a 72 hour stool and a 3-day weighed diet record collection performed after both Study Visit #1 and #2. Collection of stool will begin 24 hours after dietary records are started. All subjects will remain on their normal diet during stool collection. This includes the normal meals, snacks, and tube feeds that they typically receive. All subjects will receive a home collection kit and detailed instructions on stool collection. Stool collections will be performed at home and returned to CHOP upon completion. Subjects who are in diapers can either use plastic wrap to line the diaper or a urine collection bag secured around the anus for stool collection. They will then transfer stool from the plastic wrap or the collection bag to a stool collection container. All materials, including hand gloves, will be provided to ensure safe and accurate stool collection. All stool will be frozen until the time of analysis. Total fat content of the stool will be determined by a gravimetric method (Mayo Medical Laboratories, Rochester, MN). Total dietary intake of fat will be determined from the 3-day weighed food records. CFA % will be calculated based on determining the grams of fat consumed and the grams of fat excreted²⁷. CFA % will be compared for each subject before and after administration of pancreatic enzymes.

Coefficient of nitrogen absorption (CNA): The coefficient of nitrogen absorption (CNA %) will be calculated based on a 72 hour stool and a 3-day weighed diet record collection performed both at Study Visit #1 and #2. Collection of stool will begin 24 hours after dietary records are started. All subjects will remain on their normal diet during stool collection. This includes the normal meals, snacks, and tube feeds that they typically receive. Subjects will receive materials and instructions for proper stool collection. All samples will be collected at home and returned to CHOP. Stool will be frozen until the time of analysis. Total nitrogen content of stool will be determined by a gravimetric method (Mayo Medical Laboratories, Rochester, MN). Total dietary intake of nitrogen will be determined from a 3-day weighed food record. CNA % will be calculated based on grams of nitrogen consumed and grams of nitrogen excreted²⁷. CNA % will serve as a measure of protein absorption. CNA % will be compared for each subject before and after administration of pancreatic enzymes.

Bomb calorimetry (BC): Bomb calorimetry is a measure of energy loss in stool. This will be determined based on a 72-hour stool collection (Covance Labs, Madison, WI) performed on each subject before and after administration of pancreatic enzymes. All subjects will remain on their normal diet during stool collection. This includes the normal meals, snacks, and tube feeds that they typically receive. All samples will be collected at home, returned to CHOP, and frozen until the time of analysis. BC measures the heat of combustion of a reaction and in particular, measures the energy given off by a stool sample that is burned²⁸. As a result, it provides a measure of fecal energy loss in kcal/g stool. The energy loss from stool will be compared in each subject before and after administration of pancreatic enzymes.

Malabsorption blood test (MBT): This test will be performed on the MBT/CCK cohort only. These subjects will have the option to decline the MBT. The MBT is a measure of intestinal fat absorption and pharmacokinetic analyses yields primary outcomes from this test. The MBT involves consumption of an 8 ounce (oz) test meal that contains about 580 calories, 32.4 g of fat, and 50% calories from fat. Specifically, the fats contained in the test meal are pentadecanoic acid (PA), a free fatty acid, and triheptadecanoic acid (THA), a triglyceride with three molecules of heptadecanoic

saturated fatty acids bound to glycerol. THA requires hydrolysis by pancreatic lipase in the intestinal lumen prior to intestinal absorption. The MBT test meal is administered after the subject has fasted for 12 hours and eliminated dairy from the diet for 24 hours. The meal is prepared just prior to consumption and is composed of 64 g vanilla Scandishake (Axcan, Scandipharm, Birmingham, AL), 6 oz Silk light **vanilla** soy milk, **0.5 ounces of Hershey's chocolate syrup**, 10 milliliters microlipid (www.nestle-nutrition.com), PA, and THA. An indwelling catheter is placed in the subject prior to consumption of the meal. Blood is drawn at baseline (0 hour) and then following ingestion of the test meal at Hour 1, 2, 3, 4, 5, 6, 7, and 8. The meal should be consumed within 5 minutes following the baseline blood draw. From the samples of blood, serum PA and heptadecanoic acid (HA) levels are assessed by gas-liquid chromatography (GC). After the blood draw at Hour 6, subjects are provided a 1000 kcal, low fat (12 g) lunch meal. They are also able to consume zero-calorie and caffeine-free beverages without limit during the MBT.

Subjects in the MBT group who elect to have the MBT will have a MBT at baseline and again following administration of pancreatic enzymes. If subjects are on pancreatic enzymes prior to study enrollment, after consultation with their medical team, they will be asked to discontinue pancreatic enzymes three days before their study visit #1 until the end of the first 72 hour stool collection. For the second MBT that will be performed on pancreatic enzymes, subjects will take enzymes for 4 days and the MBT will be scheduled on day 5. Following this, they will continue to take pancreatic enzymes until the second 72-hour stool collection is complete. Please see **Table 3** for details of the MBT protocol. Subjects in the non-MBT group will not have a MBT performed.

Plasma samples to measure PHA and TA levels will be analyzed by GC. Using methods from Bligh and Dyer, total lipids are extracted from 200 μ l of plasma^{7,29}. Fatty acids are methylated in the lipid extract and fatty acid methyl esters are then extracted into iso octane. 1 μ l of sample is then injected into a GC column for analysis using a Hewlett-Packard 5890 series II gas chromatograph with a programmable cool on-column capillary inlet, flame ionization detector (FID), and HP7673 auto sampler/injector. Chromatographic data collection and analysis is via a serial connection to a computer that runs ChromPerfect Spirit™ chromatography data system (Justice Laboratory Software, Denville, NJ). The column used is a CP-Sil 88 for FAME, 100 m (L) x 0.25 mm (ID) x 0.25 μ m (film thickness) (Agilent Technologies, Inc., Santa Clara, CA) with a 1 m (L) x 0.53 mm (ID) deactivated precolumn. Calibration curves are generated based on injections of methyl PA, methyl HA, and methyl tridecanoate injections. Inter-assay variability (%CV) for the measurement of PA in samples with low, medium, and high concentrations (1.30, 2.99, and 6.70 mg/dL) has been shown to be 2.9%, 2.6%, and 3.1%, respectively⁷. Inter-assay variability for the measurement of HA (0.56, 1.29, and 3.05 mg/dL) in the samples has been shown to be 2.6%, 4.0%, and 3.9%, respectively⁷.

Primary outcomes for the MBT include pharmacokinetic analyses of PA and HA, which includes comparison of the absorption curves, maximum plasma concentration (C_{max}), area under the curve, percent absorption of plasma PA and HA concentrations, and the HA/PA ratio between each subject in the MBT cohort before and after administration of pancreatic enzymes.

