6.3.1 Efficacy Analysis

Statistical Analysis: **H1, H2, and H3:** Descriptive statistics for CFA, CNA, and BC outcomes (mean, standard deviation, median, range, 95% CI) will be calculated for the SBS cohort before and after PERT administration with paired t-tests or Wilcoxon sign rank tests depending on skewness of data. For the MBT outcomes, a moment-based pharmacokinetic (PK) analysis will be performed based on non-compartmental methodology using WinNonLin version 9.1 (Pharsight, Cary, NC). Baseline (C_0) and maximum (C_{max}) plasma concentrations are calculated, and area under the curve from time zero to eight hours (AUC) is calculated using the linear trapezoid method. PK parameters can then be compared between treatment groups using a paired t-test or Wilcoxon signed rank test as appropriate. To describe HA exposure relative to that of PA, the ratio of the HA to PA C_{max} (C_{max} HA/PA) and AUC (AUC HA/PA) is calculated for each subject after molar transformation and dose-normalization of exposure metrics⁷. Alternately, population PK analyses for repeated-measures endpoints can be conducted via nonlinear mixed-effects modeling with a qualified installation of the nonlinear mixed-effects modeling (NONMEM) software, Version VII, Level 2.0 (ICON

Development Solutions, Hanover, MD⁸. Using this method, population PK modeling is conducted by simultaneously fitting structural PK models to both PA and HA concentrations⁹.

In exploratory analyses, we will compare the estimates of percent fat absorption from the MBT with both the CFA% from the 72-hour fecal fat and diet analysis and the BC results (energy loss in the stool). We will compare the methods for detection of fat malabsorption as measured by CFA% and BC with fat absorption as measured by MBT for the subjects before and after pancreatic enzyme medication use. A correlation analysis will be conducted to evaluate the performance of the MBT relative to that of the CFA%. HA and PA C_{max}, AUC, and HA/PA ratios will be plotted against CFA% or BC caloric loss to explore the relationship between the two tests. Any relationships observed in the plots will be further explored using correlation analysis and appropriate regression analysis as dictated by the observations.

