A secondary hypothesis (**H2**) in the study is: 2) the CNA and BC will detect changes in enteral protein absorption and stool energy losses, respectively, with PERT administration in subjects with SBS. There is limited data on CNA in SBS. One study² found that subjects with SBS had a CNA of about 47%. From the literature on CF, Trapnell et al⁵ reported an increase in CNA from $49.9 \pm 1.9\%$ to $85.1 \pm 1.9\%$ after administration of PERT. Borowitz et al⁴ reported a similar increase in both CFA and CNA following PERT, with CNA specifically increasing from as low as 57% to 74.6% following administration of PERT. Ramesh et al³² studied adults patients with CP and demonstrated that PERT resulted in a significant increase in CNA from $79 \pm 8.9\%$ to $85.5. \pm 3.8\%$ (change of $6.5 \pm 7.9\%$). Similar to CFA, for CNA, 22 subjects will have 80% power to detect a difference in means of 9% (increase in CNA% from 85 to 94% after PERT administration), assuming a SD of differences of 14%, using a paired t-test with $\alpha = 0.05$ two-sided significance level.

For the BC method, there is limited information for typical variability in calories lost in stool in either healthy subjects or those with malabsorption diagnoses. It has been reported that patients with SBS can have fecal energy losses as high as 1609 ± 561 kcal/day². Using 72-hour stool assessments, Wierdsma et al²⁸ has recently reported an average daily energy loss of 213 ± 66 kcal in 23 healthy adults. If we assume that approximately 200 kcal/day are lost in the stool of healthy subjects, 21 subjects in each group will have 80% power to detect a difference in means of 50 kcal (the difference in BC between a healthy group mean of 200 and a CP group mean of 250 kcal lost in stool) assuming that the common SD is 56 using a t-test with $\alpha = 0.05$. For BC, 22 subjects will have 80% power to detect a difference in means of 36 (decrease from 250 to 214 kcal/day in the stool), assuming a SD of differences of 56, using a paired t-test with $\alpha = 0.05$ two-sided significance level.

We expect no more than 20% attrition in this study given a relatively short time period between study visit #1 and study visit #2. By enrolling 26 subjects with SBS, we can account for attrition and also allow for the possibility of greater variability in the CFA, CNA, and BC outcomes within the SBS cohort for which we have had no previous experience.

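### Bomb calorimetry is described per gram of stool but powered per day, and the plan never says which is tested

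*Combined protocol and SAP*

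**What the plan says.** Section 5.2.2 bases BC on a 72-hour stool collection in each period. Of the assay, and then in a new sentence of the comparison off and on enzymes, it says that "it provides a measure of fecal energy loss in kcal/g stool. The energy loss from stool will be compared in each subject". The sentence on the comparison names no unit and gives no formula, and nothing says whether the gram is wet or dry. For CFA and the coefficient of nitrogen absorption (CNA), the same section does say how the outcome is derived, from grams consumed and grams excreted.

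H2, in the synopsis and in Sections 2.2.1 and 6.2, is about energy lost in stool. Section 6.4 sets the BC effect as a "decrease from 250 to 214 kcal/day in the stool", with an SD of differences of 56 and 22 subjects. The SBS and healthy reference values it cites are also daily losses.

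Section 6.3.1 (Efficacy Analysis) reads "Descriptive statistics for CFA, CNA, and BC outcomes (mean, standard deviation, median, range, 95% CI) will be calculated", with a paired t-test or Wilcoxon test, and gives no unit for BC. Later it says that malabsorption blood test results "will be plotted against CFA% or BC caloric loss". Table 1 lists fecal bomb calorimetry but not stool weight.

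**The concern.** The only unit given where BC is described differs from the unit in which it is powered, and it does not measure what H2 asks. Energy lost per day is energy density multiplied by stool mass per day, so density alone follows energy loss only if mass stays constant. In short bowel syndrome that cannot be taken for granted: the protocol itself describes watery stool (Section 1.5) and plans for rising stool or ostomy output (Sections 4.6 and 9.4.2).

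An analyst who follows Section 5.2.2 literally could report no BC effect although the planned reduction occurred, or a BC gain although no less energy was lost. With the tested unit left open, it could also be settled after the data are seen. BC is one of the two outcomes named in H2 and has its own power statement.

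**Working it through.** **1. The plan's own figure.** Inputs from Section 6.4: difference 36 kcal/day, SD of differences 56, n = 22, paired t-test, two-sided alpha 0.05.

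- Noncentrality = (36/56) × √22 = 3.02, with 21 degrees of freedom.
- Power from the noncentral t distribution = 82.0%, against 80% stated.
- The smallest n for 80% power is 21. The difference detectable with 80% power at n = 22 is 35.1 kcal/day.

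The figure reproduces, but it is a kcal/day figure. There is no power statement for kcal/g.

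**2. Relation between the units.** Let E be the on/off ratio of energy lost per day and M the on/off ratio of stool mass per day. Because kcal/day = kcal/g × g/day, the on/off ratio of kcal/g is E/M. This needs no baseline weight and no SD.

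**3. Numbers.** The planned effect gives E = 214/250 = 0.856, a fall of 14.4%. The documents give no stool masses, so the mass changes below are assumed, to show a range.

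| Change in energy per day | Change in stool mass | E/M | Change in kcal/g |
|---|---|---|---|
| −14.4% | none | 0.856/1.00 = 0.856 | −14.4% |
| −14.4% | −5% | 0.856/0.95 = 0.901 | −9.9% |
| −14.4% | −10% | 0.856/0.90 = 0.951 | −4.9% |
| −14.4% | −14.4% | 0.856/0.856 = 1.000 | 0% |
| −14.4% | −20% | 0.856/0.80 = 1.070 | +7.0% |
| none | +10% (wet) | 1/1.10 = 0.909 | −9.1% |

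The same treatment effect in kcal/day can therefore appear in kcal/g as the full fall, as nothing, or as a rise. A density per wet gram can also fall through dilution alone.

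**4. Power in kcal/g (illustrative only).** The documents give no SD for kcal/g. With n = 22 and the same test, two assumed SDs of the relative change give:

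| Fall in kcal/g | SD 22.4% (56/250 carried over) | SD 10% |
|---|---|---|
| 9.9% | 51% | 99% |
| 4.9% | 16% | 59% |
| 9.1%, no true change in energy loss | 44% | 98% |

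The entries are the chance of a significant result. They depend so heavily on the SD that none can serve as an estimate.

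**The case against.** The strongest reply is that kcal/day is plainly intended. The kcal/g sentence describes what the calorimeter yields for a burned sample. The sentence that says what is compared names no unit. H2's wording, the caloric-loss phrase in Section 6.3.1, the 72-hour collection and the reference values in Section 6.4 all point to a total. On that view the plan has one endpoint with an unwritten conversion step, rather than two rival endpoints. This stands as a reading of intent. It does not supply the definition: the only unit in the outcome section remains the density, and the analysis section does not correct it.

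A reader might infer that stool mass is not collected, so that kcal/day could never be recovered. The documents do not support that. CFA and CNA need total grams of fat and nitrogen excreted over 72 hours, which implies that the collection is quantified. BC goes to a different laboratory from fat and nitrogen, and weighing before the stool is divided is not described, but that does not show the mass is lost. The conversion is feasible and unspecified.

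A reader might also take the 51%, 16% or 44% in the working as the expected performance of a kcal/g test. They are not, because they rest on an SD borrowed from kcal/day, which also contains variation in stool mass.

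Finally, BC is a secondary measure in an exploratory, proof-of-concept study. That limits the consequence and stands.

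**Conclusion.** The BC outcome is wrong as written. Its stated unit conflicts with H2 and with the power basis, no conversion is given, and the tested unit is never fixed. If kcal/g is tested, the planned 14.4% reduction can show as anything from −14.4% to +7.0% as the fall in stool mass goes from 0% to 20%, and a 10% rise in wet mass alone gives an apparent 9.1% reduction. These results are exact algebra given the mass changes, which are assumed. If stool mass is stable, the two units agree and nothing is lost. No power or false-positive rate for kcal/g can be drawn from the documents.

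The primary CFA analysis is not affected, and the BC power figure in Section 6.4 is right on its own inputs. The point is worth correcting because H2 could otherwise be answered on a variable that does not measure it.

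**What to change.** In Section 5.2.2 (Bomb calorimetry), replace the kcal/g sentence with:

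> *The total 72-hour collection will be weighed and the weight recorded. BC outcome = kcal/g × total stool weight (g, on the same wet or dry basis as the assay) / collection days = fecal energy loss in kcal/day.*

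In Section 6.3.1 (Efficacy Analysis), add:

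> *H2 for BC will be tested on the paired change in kcal/day; kcal/g and stool weight will be described only.*

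The cost is two pieces of wording and one or two case report form fields per collection, with no extra sample, visit or subject. The downside is that kcal/day, unlike kcal/g, falls when stool is missed in a home collection, so incomplete collections will matter more to the result.
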